13.	APPENDICES.....	72
13.1	APPENDIX 1: Summary of Changes for Previous Protocol Amendments.....	72
14.	ATTACHMENTS	82
14.1	ATTACHMENT 1: Child Pugh Classification	83
14.2	ATTACHMENT 2: Kansas City Cardiomyopathy Questionnaire.....	84
14.3	ATTACHMENT 3: Cardiac Event Recommendations and Management	88
14.4	ATTACHMENT 4: Study Drug Dose and Dosing Table	89
14.5	ATTACHMENT 5: Patient Diary of Daily Heart Rate and Blood Pressure Readings	91

ABBREVIATIONS

6MWT/D	6-minute walk test/distance
AE	adverse event
ANCOVA	analysis of covariance
BA	bioavailability
BE	Bioequivalence
BID	Twice daily
BMI	body mass index
BUN	blood urea nitrogen
CABG	coronary artery bypass graft
CDER	Center for Drug Evaluation and Research
CFR	Code of Federal Regulations
CK	Creatine kinase
C _{max}	maximum plasma concentration
C _{min}	minimum plasma concentration
CRA	Clinical Research Associate
eCRF	Case Report Form
CRO	Contract Research Organization
eCRF	electronic case report form
eGRF	estimated glomerular filtration rate
ECG	electrocardiogram
EMA	European Medicines Agency
FDA	Food and Drug Administration
GCP	Good Clinical Practice
HCG	human chorionic gonadotropin
HFpEF	heart failure with preserved ejection fraction
HIPAA	Health Insurance Portability and Accountability Act
IB	Investigator's Brochure
ICH	International Conference on Harmonisation
IND	Investigational New Drug
IRB	Institutional Review Board
ITT	intention-to-treat
IV	intravenous
IWRS	Interactive Web Response System

LNH	Low, Normal, High
MedDRA	Medical Dictionary for Regulatory Activities
MHRA	Medicines and Healthcare Products Regulatory Agency (UK)
NDA	New Drug Application
PD	Pharmacodynamic
PH	Pulmonary hypertension
PK	pharmacokinetic
PP	per-protocol
QD	once daily
QID	Four times daily
QoL	quality of life
RBC	red blood cell
SAE	serious adverse event
SAP	Statistical Analysis Plan
SBP	Systolic blood pressure
SmPC	Summary of Product Characteristics
TAPSE	Tricuspid annular plane systolic excursion
TID	Three times daily
$t_{1/2}$	apparent terminal-phase disposition half-life
t_{max}	time to maximum plasma concentration
TMF	Trial Master File
WBC	white blood cell
λ_z	apparent terminal-phase disposition rate constant

STUDY SYNOPSIS

Sponsor/Company Tenax Therapeutics, Inc.				
Finished product: Oral levosimendan				
Active ingredient: (-)-(R)-[[4-(1,4,5,6-tetrahydro-4-methyl-6-oxo-3-pyridazinyl)phenyl]hydrazono]propanedinitrile				
Study code: TNX-LVO-05	Date: Version 4.1 04 June 2021			
Study title: An Open-Label Rollover Study of Levosimendan in Patients with Pulmonary Hypertension with Heart Failure and Preserved Left Ventricular Ejection Fraction (PH-HFpEF)				
Investigators and study centers: Centers previously performing study with levosimendan				
Objectives: To continue treatment levosimendan in patients who were participating in a Tenax sponsored study after completion of the parent study. Protocol Version 4.1 provides for the transition of patients receiving weekly IV levosimendan to daily oral levosimendan, providing the potential for convenience, more stable dosing, and less risk of infection.				
Methodology: This open-label rollover study is designed to allow patients to continue levosimendan treatment if the patient has tolerated treatment in a clinical study sponsored by Tenax Therapeutics Inc. (the parent study) and if, in the opinion of the Investigator, the patient may benefit from continued levosimendan treatment. Patient safety will be evaluated in accordance with institutional standards of care.				
Sample size: All patients completing the parent study and in the opinion of the Investigator, may benefit from continued treatment.				
Diagnosis and main criteria for inclusion and exclusion: Patients must meet the following criteria to be enrolled in the study: Inclusion Criteria: 
1. Provide a personally signed and dated informed consent document prior to initiation of any study-related procedures that are not considered standard of care.2. Completed double-blind therapy in a PH-HFpEF clinical study sponsored by Tenax Therapeutics, Inc				

3. May, in the opinion of the Investigator, benefit from continued levosimendan treatment.
4. Female patients of childbearing potential must agree to use a highly effective method of contraception.
5. Willingness and ability to comply with scheduled visits, treatment plan, laboratory tests and other study procedures.

Exclusion Criteria:

1. Discontinued treatment in the parent study for any reason other than study completion or Sponsor termination of the study.
2. Pregnant or breastfeeding women.
3. Local access to commercially available levosimendan
4. Inability to comply with planned study procedures
5. Patients with scheduled lung or heart transplant or cardiac surgery
6. Dialysis developed since enrollment in parent study (either hemodialysis, peritoneal dialysis, continuous venovenous hemofiltration, or ultrafiltration)
7. Estimated glomerular filtration rate (eGFR) <30 mL/min/1.73m²
8. Liver dysfunction with Child Pugh Class B or C (see [Attachment 1](#))
9. Evidence of systemic bacterial, systemic fungal, or viral infection refractory to treatment
10. Weight > 150kg
11. Systolic blood pressure (SBP) cannot be managed to ensure SBP > 100 mmHg at initiation of study drug
12. Heart rate >100 bpm with study drug, persistent for at least 10 minutes at screening.
13. Hemoglobin < 80 g/L
14. Serum potassium < 3.0 mmol/L or > 5.5 mmol/L at baseline that is unresponsive to management.

Investigational product, dose, and mode of administration:

Patients will receive levosimendan at the same dose and schedule they were administered at the conclusion of the parent study. Ongoing patients will be transitioned from weekly IV levosimendan administration to daily oral levosimendan administration up to 4 mg, as tolerated, for the remainder of the study.

Duration of treatment: Patients will continue receiving levosimendan in this Open-Label Extension Study, TNX-LVO-05, and continue in the study for 3 years following transition to oral levosimendan or termination of the trial by the patient or physician decision.

Criteria for Evaluation: Primary Endpoint: 
• Incidence and severity of adverse events (AEs), clinical laboratory tests (hematology, chemistry), physical examination, vital signs (blood pressure [BP] and pulse rate [PR]) and 12-lead electrocardiogram (ECG) values. Secondary Endpoints: Assessed at Weeks 3, 6, 12, 24, 48, and yearly through Follow-up/termination visit: 
• 6-minute walk test (6MWT)• Patient global assessment (Kansas City Cardiomyopathy Questionnaire (KCCQ) instrument)• Physician's Assessment of Functional Class• Clinical Events: Death and hospitalizations
Evaluation and statistical methods: Safety and efficacy data will be summarized using descriptive statistics. Formal statistical comparisons will not be performed.

TIME AND EVENTS SCHEDULE

Procedure or Assessment	Ongoing Protocol	Levosimendan IV to Oral Transition ¹⁰					Ongoing Protocol ¹¹	
	Final Visit in Parent Study	Week 0 ¹	Week 2 ^{1,5}	Week 4 ^{1,5}	Final Visit, Week 6 ^{1,4}	Patients titrated at Week 6 should return on Week 8	Office Visits ⁴ (Weeks 3, 6, 12, 24, 48 and yearly) since enrolling in study	Follow-up Visit (termination visit)
Informed Consent	X	X						
Confirm Eligibility Criteria	X							
Physical Examination	X	X			X ⁶	X		X
Body Weight	X	X					X	X
Serum Chemistry and Hematology (Local Lab) ⁷	X	X			X ⁶	X	X	X
Child Pugh Class ⁷	X							X
Vital Signs	X	X	X	X	X	X	X	X
Pharmacokinetic Sample		X ²		X	X ²	X ²		
Electrocardiogram (ECG)	X	X			X ⁶	X		X
Levosimendan Administration (oral) / Dose Titration ³		X	X	X	X ⁴			
NYHA Functional Class	X	X			X ⁶	X	X	X
6 - Minute Walk Test	X	X			X ⁶	X	X	X
Adverse Events/SAEs ⁸	X	X	X	X	X	X	X	X
Concomitant procedures and medications	X	X	X	X	X	X	X	X
KCCQ Assessment ⁹	X	X			X ⁶	X	X	X

Footnotes for Time and Events Schedule

1. Visits will be scheduled 7-9 days following completion of the levosimendan IV dose and every 14 days through the oral levosimendan transition (+/- 48 hrs); at the Investigator's discretion, Week 2 and 4 visits may be performed remotely.
2. Blood sample to be taken prior to the patient's daily dose of oral levosimendan.
3. The first dose of oral levosimendan to be taken 7-9 days after the patient's final weekly IV levosimendan dose. Once oral levosimendan begins, subjects must completely discontinue weekly levosimendan infusions. Patients will begin a daily dose regimen of 1mg daily and titrated at 1mg increments every 2 weeks, as tolerated.
4. At the investigator's discretion, patients that have not demonstrated an adequate response to drug therapy and a tolerance to the 1mg levosimendan TID may be titrated to 1mg QID. Patients that have not tolerated 1 mg levosimendan TID should be down titrated to 1mg BID. All patients that are titrated at Week 6 should return for a Week 8 visit.
5. Due to the COVID-19 pandemic, the investigator may have a phone conversation with the patient rather than having the patient come in for an office visit. The phone conversation should include the following, as reported by the patient; adverse events, concomitant medications (new or changed), concomitant procedures, and blood pressure & heart rate (use provided home blood pressure cuff).
6. If a patient is up or down titrated and therefore scheduled for a Week 8 visit, these procedures do not need to be performed at Week 6.
7. Local labs will be drawn (including NT-proBNP). Child-Pugh Class is only required for patients with documented liver disease.
8. During routine visits and throughout a participation in the study, patients should be queried for any new or changes to AEs, concomitant medications, concomitant procedures, hospitalizations, and/or emergency room visits
9. The KCCQ should be reviewed as soon as possible after the patient completes the questionnaire to ensure all questions have been answered. The patient should be given the appropriate time to complete the questionnaire and to ask any questions they may have.
10. These visits only pertain to patients who have consented to the transition from IV to oral levosimendan.
11. All patients will continue to follow the Ongoing Protocol Assessments. For patients who are on IV levosimendan, these visits will resume for two years based on the date the patient originally entered the TNX-LVO-05 study (e.g., the final visit in the parent study, TNX-LVO-04)

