1.3.1 Preclinical Information

Levosimendan's activity is mediated through unique mechanisms of action, including:

- Increased cardiac contractility by calcium sensitization of troponin C. (11-14)
- Vasodilation through the opening of potassium channels. (15-18)
- Cardioprotective effects via potassium channel opening in mitochondria. (19-22)

Levosimendan has an active metabolite that extends its effects well beyond the infusion period. Following intravenous or oral dosing, levosimendan is reduced by intestinal bacteria to form OR-1855 (limited activity) that is acetylated to form OR-1896, an active metabolite. While the parent half-life is approximately 1 hour and cleared a few hours after the end of intravenous infusion, OR-1896 has a prolonged half-life of 70-80 hours in heart failure subjects with roughly equal exposures of OR-1855 and OR-1896 maintained through deacetylation/ acetylation pathways. The OR-1896 metabolite has been shown to retain similar hemodynamic and pharmacologic properties of levosimendan and maintain roughly

equivalent effects to levosimendan in preclinical models. This activity occurs despite considerably lower plasma concentrations relative to levosimendan, an apparent result of a large percentage of unbound OR-1896 in circulation. (22-27). Thus, in extended repeated dosing, levosimendan is essentially an active prodrug to an active metabolite moiety, OR-1896.

Levosimendan has been shown to be a potent and selective phosphodiesterase-3 (PDE3) inhibitor *in vitro*. The drug is PDE3 selective with a PDE3/PDE4 inhibition ratio of 10,000. (15, 49). However, both isozymes must be inhibited in cardiomyocytes to exert an effect on the cAMP concentration and inotropic effects. The classical PDE inhibitors (i.e. milrinone, enoximone, and amrinone) inhibit both PDE3 and PDE4 at therapeutic concentrations (e.g. milrinone selectivity for PDE3 vs PDE4 is as low as 17-fold), which accounts fully for their inotropic effect.

OR-1896 is equipotent to levosimendan in its inotropic effects in whole cardiomyocytes and isolated contractile apparatus preparations. However, OR-1896 is profoundly less potent in the inhibition of both PDE3 and PDE4 isozymes. This supports the hypothesis that the main component of the inotropic effect for both levosimendan and OR-1896 is a result of their binding to troponin C and not through PDE inhibition. (49)

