5.5.2 Dose Adjustment

The oral levosimendan dose may be decreased in 1 mg increments or interrupted as clinically warranted if the subject has hypotension, tachycardia, or signs or symptoms consistent with hypovolemia (e.g., low SBP, decreasing urine output with rising blood urea nitrogen [BUN] and serum creatinine). Record the date of discontinuation or down titration. Patients should be monitored closely until clinically stable.

Missed doses should be skipped and not taken as a double dose at the next dosing time.

Refer to the following subsections for additional guidance on events that require study drug discontinuation or dosage adjustment, permanent discontinuation, and re-initiating study drug in subjects in whom clinical stability has been restored.

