7.1.4 IV-Oral Transition Week 6 – Final Visit

During this visit, the following procedures will be performed:

- Vital signs and ECG
- Physical Exam
- Hematology and chemistry blood samples
- Assess adverse events
- Pharmacokinetic sample
- 6MWT
- NYHA Functional Class
- Kansas City Cardiomyopathy Questionnaire (KCCQ)

Once a patient transitions to oral levosimendan, all references in this protocol to the administration of IV levosimendan, will no longer apply for that patient. All study drug and ancillary supplies related to the administration of IV levosimendan will be returned to the central pharmacy for destruction.

7.1.5 IV-Oral Transition Week 8

This visit is only required for patients who titrated (up or down) at the Week 6 visit.

During this visit, the following procedures will be performed:

- Vital signs
- Physical Exam
- Hematology and chemistry blood samples
- Assess adverse events
- Pharmacokinetic sample
- 6MWT
- NYHA Functional Class
- Kansas City Cardiomyopathy Questionnaire (KCCQ)

The Physical Exam, 6MWT, NYHA Functional Class, and KCCQ do not need to be performed for patients who are scheduled for a Week 8 visit, due to either up or down titration of study drug.

Following the Final Evaluation (either Week 6 or Week 8), patients will continue to visit the investigational site at weeks 3, 6, 12, 24, 48, and yearly through the Follow-Up Visit (at termination) and/or Termination visit. These visit windows will be based on the date the patient originally enrolled in the TNX-LVO-05 study. Visits that overlap may be combined into one visit.

Patients unable to return at the scheduled Week 6 or 8 visit, may have their final visit extended.

7.2 Weeks 3, 6, 12, 24, 48, and yearly through the Follow-up and/or Termination

visit (Office Visits)

Visits at Weeks 3, 6, 12, 24, 48, and yearly through the Follow-up and/or Termination visit should be performed within ± 72 hours of the scheduled weekly visit. These visits may be performed at the investigator's office. For any patients who remain on IV levosimendan, the Follow-Up Visit (at termination) will be calculated as the earlier of two years from the subject's date of entry into the TNX-LVO-05 Study or as soon as possible after study discontinuation, but within 1 week.

During this visit, the following procedures will be performed:

- Vital signs
- Physical Exam
- Hematology and chemistry blood samples
- Body Weight
- 6MWT
- Kansas City Cardiomyopathy Questionnaire (KCCQ)

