3.4.1 Primary Endpoints

The primary endpoints (Safety measures) are as follows:

- Incidence and severity of treatment-emergent adverse events (TEAEs),
- Incidence and severity of abnormal clinical laboratory test results (hematology, chemistry),
- Incidence of abnormal physical examination results,
- Incidence of abnormal vital sign values (blood pressure [BP] and pulse rate [PR]), and
- Incidence of abnormal 12-lead electrocardiogram (ECG) results or values.

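### Schedule footnote 6 conflicts with Sections 7.1.4 and 7.1.5 on Week 6 tests in patients titrated at that visit; if it is followed, scheduled transition exam, lab and ECG results on 3 mg/day come only from patients whose dose was not changed

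*Protocol*

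**What the plan says.** **Schedule.** In the protocol's Time and Events Schedule, the Week 6 entries for physical examination, serum chemistry and hematology, and ECG carry mark 6, as do NYHA class, 6MWT and KCCQ. For a patient moved up or down, footnote 6 reads "titrated and therefore scheduled for a Week 8 visit, these procedures do not need to be performed at Week 6". Vital signs, adverse events and the PK sample carry no such mark. Weeks 2 and 4 schedule no exam, labs or ECG. Week 8, for titrated patients only, has all three. The ongoing office visits have labs but no ECG.

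**Who is titrated at Week 6.** Footnote 4: "Patients that have not tolerated 1 mg levosimendan TID should be down titrated to 1mg BID". Under the same footnote, patients who tolerate TID without an adequate response may go up to 1 mg QID. Section 5.5.1 starts TID (3 mg/day) after 4 weeks.

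**Body text.** Section 7.1.4 lists ECG, physical exam and "Hematology and chemistry blood samples" at Week 6 with no exception. Section 7.1.5 has its own waiver for patients due at Week 8. It names physical exam, 6MWT, NYHA class and KCCQ only, and does not say which visit it applies to. The Week 8 list in Section 7.1.5 has no ECG.

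**Analysis.** SAP 3.4.1 has five primary safety components: adverse events, labs, physical exam, vital signs and ECG ("Incidence of abnormal 12-lead electrocardiogram (ECG) results or values"). Protocol 10.8 summarizes labs, vital signs and ECG by treatment group and visit. SAP 3.2.1 summarizes by IV period, oral period and total. SAP 3.5.2 to 3.5.5 present clinically significant labs, vital signs, abnormal ECGs and exams as patient listings.

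**The concern.** Under footnote 6, whether a safety test is done at Week 6 depends on what happened to the patient on the dose being tested. Patients who did not tolerate 3 mg/day are moved down, and their exam, labs and ECG at that dose become optional. Patients with an inadequate response are moved up, and theirs become optional too. Week 6 is the only transition visit that schedules these tests on 3 mg/day before the dose decision, so no later visit recovers them.

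Section 5.5.2 gives "decreasing urine output with rising blood urea nitrogen [BUN] and serum creatinine" among its examples of signs that can prompt an oral dose reduction. Under footnote 6, the scheduled blood test that would document such a change need not be done in the patients who are reduced.

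At stake is how complete three of the five primary safety components are, and whether sites reading different parts of the protocol collect the same data.

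**Working it through.** The plan states no figure on this point, so the check sets the passages side by side and adds one calculation.

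**Step 1. Exam, labs and ECG required at Week 6, on 3 mg/day**

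| Patient at Week 6 | Schedule with footnote 6 | Section 7.1.4 list | Section 7.1.5 waiver, read as applying to Week 6 |
|---|---|---|---|
| Dose unchanged | exam, labs, ECG | exam, labs, ECG | exam, labs, ECG |
| Moved down or up | none of the three | exam, labs, ECG | labs, ECG |

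Vital signs, adverse events and PK are required in every cell. For a titrated patient, the primary components not required at Week 6 number 3 of 5 under footnote 6, 0 of 5 under Section 7.1.4 and 1 of 5 (the exam) under Section 7.1.5.

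**Step 2. Transition ECGs after oral dosing starts, for a titrated patient**

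- Schedule alone: none at Week 6, one at Week 8.
- Sections 7.1.4 and 7.1.5 alone: one at Week 6, none at Week 8.
- Footnote 6 at Week 6 with the Section 7.1.5 list at Week 8: none.

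The ongoing office visits schedule no ECG, and Section 2.3 places the Follow-Up Visit after study drug discontinuation. Under the third combination, no ECG is scheduled at all while the patient takes oral drug.

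**Step 3. Can Week 8 stand in for Week 6?** Section 1.3.1 states that "OR-1896 has a prolonged half-life of 70-80 hours in heart failure subjects". Week 8 is 14 days, or 336 hours, after the change. The fraction of the shift completed is 1 − 2^(−336/h):

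- h = 70: 1 − 2^(−4.80) = 0.964
- h = 75: 1 − 2^(−4.48) = 0.955
- h = 80: 1 − 2^(−4.20) = 0.946

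Assume exposure proportional to dose and Week 6 at steady state. A patient moved from 3 to 2 mg/day is then at 2 + 2^(−336/h) = 2.04 to 2.05 mg/day-equivalent at Week 8. Week 8 results describe the new dose.

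**Step 4. Size.** The documents give no rate of titration at Week 6 and no rate of abnormal results. Suppose a fraction f is titrated, with abnormal-result rate p_c against p_s in patients left unchanged. The rate in all patients is f·p_c + (1 − f)·p_s, while the tested patients show p_s. Every input below is an assumption:

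- p_s = 10%, p_c = 20%, f = 10%: 0.1 × 0.20 + 0.9 × 0.10 = 11%
- p_s = 10%, p_c = 40%, f = 50%: 0.5 × 0.40 + 0.5 × 0.10 = 25%
- p_c = p_s: no difference

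The range therefore runs from no gap to 25% against 10%. If p_c were below p_s, which is conceivable when most titrated patients go up after tolerating TID, the sign would reverse. This shows how the selection works; it does not estimate its effect here.

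**The case against.** The strongest reply is that the loss of ECG and labs follows from only one of the conflicting texts. Section 7.1.4 requires both at Week 6, and the Section 7.1.5 waiver does not name them. That is correct, and it is why the point is a conflict to reconcile. It does not remove the problem: Section 8 tells sites to follow the Time and Events Schedule, so footnote 6 may well be the text applied.

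A reader might go further and infer that the primary safety incidences at 3 mg/day will be biased toward looking safe. The documents do not support that:

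- The SAP plans no incidence by mg/day. It pools the oral period and lists labs, ECG and exam. The treatment/dose group in SAP 3.5 is not defined by mg/day, and the SAP's table list has no lab, ECG or exam table.
- Adverse events and vital signs are collected at Week 6 in everyone. Section 1.3.6 names hypotension and tachycardia as the main safety events of interest, and patients record blood pressure and heart rate daily.
- Up-titrated patients are skipped too, so the gap is not only intolerance and its net direction is unknown.

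Nor may one infer that a down-titrated patient has no result at all. The waiver is permissive. An ongoing visit on the same day brings its own procedures (Section 7.1), including labs. Attachment 3 calls for an ECG at a validated heart rate above 120 without symptoms, and an investigator may order tests at any time. These routes may fill some gaps, but not systematically.

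Finally, Section 5.5.3 allows dose reduction at any time. Some patients who do not tolerate 3 mg/day will already be on less by Week 6, and testing everyone then recovers only part of the information. That stands as a limit on the fix.

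**Conclusion.** The point holds as a conflict between passages with a consequence for the data. Footnote 6, Section 7.1.4 and Section 7.1.5 give three different answers on the Week 6 exam, labs and ECG in titrated patients, and the schedule and Section 7.1.5 also disagree on the Week 8 ECG. If footnote 6 is followed, three of the five primary safety components have scheduled transition results on 3 mg/day only in patients whose dose was left unchanged, and Week 8 cannot replace the missing ones. The Week 8 conclusion rests on the stated half-life and on dose proportionality.

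The effect falls on the lab and ECG by-visit summaries in protocol 10.8, if they are produced, and on what the SAP's safety listings can contain. Its size cannot be derived from the documents. It should be corrected because the gap depends on tolerability and response and costs little to close.

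**What to change.** Reconcile the passages as follows:

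1. Remove mark 6 from the Physical Examination, Serum Chemistry and Hematology, and ECG rows, so that these are done at Week 6 in every patient before any dose change, as Section 7.1.4 already lists.
2. Limit the Section 7.1.5 waiver to 6MWT, NYHA class and KCCQ, and state that it refers to Week 6.
3. Add the ECG to the Section 7.1.5 Week 8 list, to match the schedule.
4. Show the dose in force with each ECG, lab and exam result in the listings. Where Week 6 tests were already omitted under footnote 6, any Week 6 summary should state how many patients were tested and how many were not, by whether the dose was unchanged, raised or lowered.

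This concerns when measurements are taken; it changes no titration or dosing rule. The cost is one ECG, one exam and one local-lab draw per titrated patient, at an office visit already attended where PK blood is drawn anyway, plus one dose field in the listings.
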